4.2.5.4 Analysis of Secondary Outcome

Plasma concentrations will be summarized by each analysis visit and scheduled time using descriptive statistic, number of non-missing observations, n below LLOQ, arithmetic mean, SD, geometric mean, geometric coefficient of variation (CV%), min, median and max. Plasma concentrations will also be listed for all subjects in the PK analysis set.

4.2.6 Secondary Endpoint- Development of ADA and ADA titer (if subjects are ADA positive) during treatment and follow-up.

4.2.6.1 Definition

Development of anti-drug antibodies (ADA) and ADA titre will be used to evaluate the immunogenicity of AZD8233. Titre evaluations are conducted only on those samples that are confirmed positive for ADA.

Treatment-induced ADA positive is defined as ADA negative at baseline and post-baseline ADA positive.

Treatment-boosted ADA positive is defined as ADA positive at baseline and boosted the pre-existing titre post-baseline (≥ 4 -fold increase).

TE-ADA positive is defined as the sum of treatment-induced ADA positive and treatment-boosted ADA positive.

TE-ADA negative is defined as ADA positive but not fulfilling the definition of TE-ADA positive.

ADA persistently positive is defined as either ADA negative at baseline and ADA positive at ≥ 2 post-baseline assessments (with ≥ 16 weeks between first and last positive) either ADA positive at last post-baseline assessment.

ADA transiently positive is defined as ADA negative at baseline, having at least one postbaseline ADA positive assessment and not fulfilling the conditions of ADA persistently positive.

4.2.6.2 Derivations

ADA parameters will be assigned to an analysis visit as defined in Section 3.3.2. The median of maximum titres is calculated based on the maximum titre for each ADA positive subject within each treatment group (including both baseline and post-baseline measurements).

Missing ADA results are considered negative for the derivation of the ADA categories. The above categories will be calculated only for subjects in the ADA analysis set.

4.2.6.3 Handling of Dropouts and Missing Data

Missing data will not be imputed and only observed values will be reported in the summary tables and listings. Treatment discontinuation visit will be mapped according to Section 3.3.2.

4.2.6.4 Analysis of Secondary Endpoint

ADA endpoints will be analyzed based on the Safety Analysis Set. The number and percentage of subjects with a positive result will be tabulated for: any time in study, baseline, any time post-baseline, and by visit and treatment group. ADA titre will be summarized descriptively as a continuous variable, only for ADA positive tests, with median, interquartile range, minimum, and maximum, at each visit.

ADA will also be summarized including the following:

- ADA positive at baseline and/or post-baseline (ADA prevalence)
- TE-ADA positive (ADA incidence)
- Treatment-induced ADA positive
- Treatment-boosted ADA positive
- TE-ADA negative
- Both baseline and post-baseline positive
- Only baseline positive
- ADA persistently positive
- ADA transiently positive
- TE-ADA positive with maximum titre > median of maximum titres

All immunogenicity parameters will also be reported in a listing for the full analysis set. Days from previous dose of IP will be calculated as the ADA date minus date of previous dose +1. Days from previous dose of IP for ADA measured during pre-treatment period will be set to missing. Listings of all subjects excluded from the ADA analysis set will also be provided. The listing will be based on all enrolled subjects.

The following figures will be also provided for complete analysis only:

- A spaghetti plot figure with individual plotted ADA-titres over time in subjects with any positive ADA-response, one graph per treatment group (including placebo).

- A boxplot on log-transformed data exploring ADA positive vs ADA negatives impact on PK concentrations, PCSK9 and LDL over time one graph per treatment group (including placebo).
- A figure showing the percentage of subjects with positive ADA results over time.

4.2.7 Other Endpoint – Injection Site Reactions

4.2.7.1 Definition

Injection site reactions (ISRs) are reported using standard AE collection criteria.

4.2.7.2 Derivations

Injection site criteria will be coded using the MedDRA version 24.0 or higher.

4.2.7.3 Handling of Dropouts and Missing Data

Imputation of partial dates and handling of missing data will be conducted as defined in Section 3.3.1.2.

4.2.7.4 Analysis of Other Endpoint

All summaries of injection site reactions will be based on the Safety Analysis Set and will be summarized by treatment group. The number and percentage of subjects with an injection site reaction and the number of events will be summarized by High Level Term (HLT) and preferred term.

Subjects with multiple events in the same category are counted once in that category. Subjects with events in more than one category are counted once in each of those categories.

4.3 Safety Analyses

The domain safety covers exposure, adverse events, clinical laboratory, vital signs, and ECG.

4.3.1 Exposure

4.3.1.1 Definitions and Derivations

Treatment exposure will be calculated in days as the treatment duration from date of first dose to date of last dose, inclusive.

$$\text{Duration of exposure (days)} = \text{last dose date} - \text{first dose date} + 1$$

4.3.1.2 Presentation

Duration of exposure will be summarized based on the Safety Analysis Set. Summaries will be presented by treatment group using the principles outlined in Section 3.3 for continuous variables.

4.3.2 Adverse Events

4.3.2.1 Definitions and Derivations

An adverse event (AE) is the development of any untoward medical occurrence in a patient or clinical study participant administered a medicinal product and which does not necessarily have a causal relationship with this treatment. An AE can therefore be any unfavourable and unintended sign (eg, an abnormal laboratory finding), symptom (for example nausea, chest pain), or disease temporally associated with the use of a medicinal product, whether or not considered related to the medicinal product.

The term AE is used to include both serious (SAE) and non-serious AEs and can include a deterioration of a pre-existing medical occurrence. An AE may occur at any time, including run-in or washout periods, even if no study intervention has been administered.

A treatment-emergent adverse event (TEAE) is defined as an AE with an onset date on or after the first dose date.

Adverse events will be coded using the MedDRA version 24.0 or higher.

Imputation of partial dates and handling of missing data will be conducted as defined in Section 3.3.1.2.

4.3.2.2 Presentation

All summaries of adverse event data will be based on the Safety Analysis Set and will be presented by treatment group. Summary tables will include TEAEs only whereas listings will include all reported AEs.

A subject-level overview of AEs (the number and percent of subjects and the number of events) will be tabulated by the treatment groups in a single table for:

- Any AE.
- AEs possibly related to study treatment.
- AEs with an outcome of death.
- AEs with outcome of death possibly related to study treatment.
- All serious adverse events (SAE).
- SAEs possibly related to study treatment.

- AEs leading to discontinuation of study treatment.
- AEs leading to discontinuation of study treatment, possibly related to study treatment.
- AEs leading to dose interruption.
- AEs leading to withdrawal from the study.

Separate AE summary tables of the number and percentage of subjects with AEs and the number of events in each of the categories above will be produced by SOC and PT.

Additionally, the following tables will be presented by SOC and PT:

- AEs by the maximum reported intensity.
- AEs by causality assessment.
- Bleeding AEs (Haemorrhages (SMQ) including both "Haemorrhage laboratory terms (SMQ)" & "Haemorrhage terms (excluding laboratory terms) (SMQ)").

Subjects with multiple events in the same category are counted once in that category.

Subjects with events in more than one category are counted once in each of those categories.

4.3.3 Clinical Laboratory, Blood Sample

4.3.3.1 Definitions and Derivations

In the assessments of hematology parameters, clinical chemistry and coagulation, the parameters to be summarized are listed in Appendix 7.2.

Clinical laboratory results will be assigned to analysis visits as described in Section 3.3.2.

Safety clinical laboratory results below the lower limit of quantification (LLOQ) for which the exact value cannot be determined will be replaced with the LLOQ.

After replacements of LLOQ, the change from baseline will be calculated for all post-baseline timepoints as the respective timepoint value minus the baseline value.

Based on the respective reference range indicators, the following flags will be applied to all laboratory assessments; 'Normal' (if the value is within the normal reference range), 'Low' (if the value is below the normal reference range) or 'High' (if the value is above the normal reference range).

eGFR

Subject's eGFR will be calculated from serum creatinine (SCr) concentration, according to the Japanese equation as follows:

$$\text{eGFR} = 194 \times \text{SCr}(\text{mg/dL})^{-1.094} \times \text{Age}^{-0.287} \times \alpha$$

where α is 1 for males and 0.739 for females.

Liver enzyme abnormalities

AST, ALT and TBL will be classified as follows:

AST and ALT:

- $<1.5 \times \text{ULN}$ (or below the LLOQ).
- ≥ 1.5 to $<3 \times \text{ULN}$.
- ≥ 3 to $<5 \times \text{ULN}$.
- ≥ 5 to $<8 \times \text{ULN}$.
- $\geq 8 \times \text{ULN}$.

TBL:

- $<1 \times \text{ULN}$ (or below the LLOQ).
- ≥ 1 to $<2 \times \text{ULN}$.
- $\geq 2 \times \text{ULN}$.

Occurrences of AST or ALT $\geq 3 \times \text{ULN}$ together with TBL $\geq 2 \times \text{ULN}$ are reported as SAE (Potential Hy's Law).

Platelet count

Platelet count will be classified as follows:

- $< \text{LLN}$
- $> \text{ULN}$

- < 50 ($10^9/L$)
- < 75 ($10^9/L$)
- < 100 ($10^9/L$)
- < 150 ($10^9/L$)
- > 30% decrease from baseline
- < 150 ($10^9/L$) and > 30% decrease from baseline

Shift to minimum value on-treatment value for platelet count will be classified as follows:

- < 50 ($10^9/L$)
- ≥ 50 and < 75 ($10^9/L$)
- ≥ 75 and < 100 ($10^9/L$)
- ≥ 100 and < 150 ($10^9/L$)
- ≥ 150 ($10^9/L$)

Missing data will not be imputed and only observed values will be reported in the summary tables and listings. Treatment discontinuation visit will be mapped according to Section 3.3.2.

4.3.3.2 Presentation

Laboratory data will be summarized based on the Safety Analysis Set. Summaries of the individual values and change from baseline will be presented by treatment group and visit according to the principles outlined in section 3.3.1. The number and proportion of patients with liver enzyme abnormalities will be summarized by treatment group and visit including a summary of the maximum recorded post-baseline value. Treatment-emergent platelet count abnormalities will be summarised by treatment group and visit, including the shift to minimum value and key subject information will be presented.

Shift tables will be presented for select laboratory parameters (clinical chemistry and hematology). An additional shift table will be presented for hematology results, displaying the percent change from baseline (i.e. the relative change). Spaghetti plots over time will be produced for platelet count, ALT, AST, and TBL, with the corresponding reference range overlaid on top. The following additional plots will be presented for platelet count only:

- Empirical cumulative distribution function curves for the absolute change from baseline to minimum value.
- A spaghetti plot of the relative change from baseline in subjects with platelet count <150 ($10^9/L$) or $> 30\%$ decrease from baseline.
- A spaghetti plot of the absolute change from baseline in subjects with platelet count <150 ($10^9/L$) or $> 30\%$ decrease from baseline.

4.3.4 Clinical Laboratory, Urinalysis

4.3.4.1 Definitions and Derivations

In the assessments of urinalysis, and urinalysis (positive dipstick), the parameters to be summarized are listed in Appendix 7.2.

Clinical laboratory results will be assigned to analysis visits as described in Section 3.3.2.

Safety clinical laboratory results below the lower limit of quantification (LLOQ) for which the exact value cannot be determined will be replaced with the LLOQ.

After replacements of LLOQ, the change from baseline will be calculated for all post-baseline timepoints as the respective timepoint value minus the baseline value.

4.3.4.2 Presentation

Laboratory data will be summarized based on the Safety Analysis Set. Summaries of the individual values and change from baseline will be presented by treatment group and visit according to the principles outlined in section 3.3.1.

4.3.5 Other Laboratory Evaluations

4.3.5.1 Definitions and Derivations

The parameters to be summarized are listed in Appendix 7.2.

Clinical laboratory results will be assigned to analysis visits as described in Section 3.3.2.

Safety clinical laboratory results below the lower limit of quantification (LLOQ) for which the exact value cannot be determined will be replaced with the LLOQ.

After replacements of LLOQ, the change from baseline will be calculated for all post-baseline timepoints as the respective timepoint value minus the baseline value.

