The screening period starts within 28 days before the randomization visit and ends on Day -4. Eligible participants will make 7 visits during the treatment period and 7 additional visits during the follow-up period. They are randomized across 3 different treatment arms in a 1:1:1 ratio for a 12-week treatment period. The planned treatment arms are AZD8233 **CCI** , AZD8233 **CCI** , and placebo. Participants will be dosed subcutaneously on Days 1, 29, and 57.

Disclosure Statement:

[Part A/Part C]

This study is single-blind with regards to treatment (AZD8233 or placebo), and blinded to the participants, site investigators, and site staff. The Sponsor will be unblinded to treatment allocation.

[Part B]

This is a parallel group treatment study in 3 arms with participants, investigators and the sponsor blinded.

Number of Participants:

[Part A/Part C]

Approximately 11 participants will be randomly assigned to the 2 study arms in each part.

[Part B]

Approximately 60 participants will be randomly assigned to the 3 study arms.

Note: “Enrolled” means a participant's, or their legally acceptable representative's, agreement to participate in a clinical study following completion of the informed consent process.

Potential participants who are screened for the purpose of determining eligibility for the study, but are not randomly assigned/assigned in the study, are considered “screen failures”, unless otherwise specified by the protocol.

Study Period:

[Part A/Part B/Part C]

Estimated date of first patient enrolled: Q4 2020

Estimated date of last patient completed: Q4 2023

Intervention Groups and Duration:

[Part A/Part C]

The screening period starts up to 28 days before the randomization visit and ends on Day -4. Eligible participants will make 8 visits during the treatment period and 8 additional visits during the follow-up period. They are randomized across 2 different treatment arms at an 8:3 ratio for a 58-day (up to Visit 9) treatment period. The planned treatment arms are AZD8233 **CCI** (Part A) / AZD8233 **CCI** (Part C) and placebo. Participants will be dosed subcutaneously on Days 1, 8 (Part A only), 29, and 57.

[Part B]

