Antidrug Antibodies	There is a potential risk for antibody formation. Emergence of ADA has been observed in a proportion of clinical study participants after repeated oligonucleotide treatment, leading to change in the PK profile. To date, no apparent association of ADA with loss of efficacy or safety findings has been observed.	Assessment of ADAs and monitoring for immunogenicity effects (including hypersensitivity reactions and ADA effect on PK/PD). Guidance on the definition of an anaphylactic reaction and the action plan that needs to be followed with regards to ADA sampling are presented in Appendix G .
Injection Site Reactions	
As with any exogenous substance, injection site reactions may occur as a response to the SC injection of AZD8233. Possible risks associated with SC administration are redness, swelling, pain, induration, and sometimes infection at the administration site. There have been reports in some ASO programs of a few cases of severe ISRs with a high incidence of discomfort to the patient that have led to withdrawal from treatment.
 
In the ongoing clinical programme for AZD8233, mild ISRs have been observed in a few participants (see Section 2.2 for details).
	Monitoring for injection site reactions
Complement Activation	
This is a known class effect of oligonucleotides and appears to be directly plasma concentration (C_{max}) driven. Monkeys are considered more sensitive to complement activation than humans (Crooke ST et al 2016).
 
In the 9-month monkey study, minimal to mild higher complement Bb was observed at ≥ 6 mg/kg/occasion at the end of the
	Assessment of complement activation around C_{max} ($C3a$ [Part A only], $C5a$, Bb)

Potential risk of clinical significance	Rationale for risk	Mitigation Strategy
	study and correlated microscopically with mononuclear cell (predominantly lymphocytic) infiltration/inflammation observed in multiple tissues, including the administration site.	

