3.3.1 General Study Level Definitions

3.3.1.1 Definition of Baseline

Unless otherwise specified, ‘baseline’ refers to the last measurement obtained before the first dose of study intervention. For lipid parameters (PCSK9, LDL-C, etc), the measure taken pre-dose at Visit 3 (Day 1) will be typically considered as baseline.

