3.3.2 Visit Window

Study visits windows are defined in the table below:

	Screening		Treatment Period							EDV	Follow-up period ^a	Final Follow-up Visit ^b
Visit Number	1	2	3	4	5	6	7	8	9		10, 11, 12, 13, 14, 15	16
Study Week			0	1	3	4	6	8	10		12, 14, 16, 18, 20, 22	24
Study Day	Days -28 to -10	Days -7 to -4	Day 1	Day 8	Day 22	Day 29	Day 43	Day 57	Day 71		Days 85, 99, 113, 127, 141, 155	Day 169
Visit Window				± 1 day	± 2 days		± 2 days	± 2 days				

Analysis Visit Windows

Analysis visit windows will be defined for the lipid parameters, ECG, anti-AZD8233 antibodies, laboratory results and vital signs which summarize values by visit. These analysis visit windows will be exhaustive so that data recorded at any time point has the potential to be summarized. Inclusion within the window will be based on the actual date and not the intended date of visit.

Analysis visit windows will be constructed such that the upper limit of the window intervals fall halfway between two scheduled visits, where the number of days between visits is odd, the additional day will be applied to the lower interval of the later date.

Table 1: Analysis visit windows for lipid parameters, laboratory parameters* and vital signs

Analysis Visits	Scheduled visit day	Analysis visit window (days)
Baseline ^a	Day -28 to Day 1	≤ Day 1
Treatment period		
Day 1	Day 1	Day 1 ^b
Week 1	Day 8	Day 2 – Day 14
Week 3	Day 22	Day 15 – Day 25
Week 4	Day 29	Day 26 – Day 35
Week 6	Day 43	Day 36 – Day 49
Week 8	Day 57	Day 50 – Day 63
Week 10	Day 71	Day 64 – Day 77
Follow-up period		

Week 12	Day 85	Day 78 – Day 91
Week 14	Day 99	Day 92 – Day 105
Week 16	Day 113	Day 106 – Day 119
Week 18	Day 127	Day 120 – Day 133
Week 20	Day 141	Day 134 – Day 147
Week 22	Day 155	Day 148 – Day 161
Week 24	Day 169	Day 162 onwards.

*Complement activation panel is collected pre-dose on Visits 12, 3, 6 and 8 only. Hs-CRP is collected at Visit 1, 8 and all follow-up visits.

^a Baseline is defined as the last measurement prior to first dose of study treatment. Pre-dose values on Day 1 qualify as baseline measurements.

^b Day 1 is defined as date of first dose of study treatment. Includes all measurements collected at Day 1 after the first dose of IP.

Table 2: Analysis visit windows for ECG

Analysis Visits	Scheduled visit day	Analysis visit window (days)
Baseline ^a	Day -28 to Day 1	≤ Day 1
Treatment period		
Day 1	Day 1	Day 1 ^b
Week 1	Day 8	Day 2 – Day 18
Week 4	Day 29	Day 19 – Day 42
Week 8	Day 57	Day 43 – Day 70

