LDL-C ^e		X	X	X	X	X	X	X	X	X	X	X
PCSK9 ^e		X	X	X	X	X	X	X	X	X	X	X

	Screening		Treatment Period							EDV	Follow-up period ^a	Final Follow-up Visit ^a
Visit Number	1	2	3	4	5	6	7	8	9		10, 11, 12, 13, 14, 15	16
Study Week			0	1	3	4	6	8	10		12, 14, 16, 18, 20, 22	24
Study Day	Days -28 to -10	Days -7 to -4	Day 1	Day 8	Day 22	Day 29	Day 43	Day 57	Day 71		Days 85, 99, 113, 127, 141, 155	Day 169
Visit Window				± 1 day	± 2 days		± 2 days	± 2 days				
Triglycerides ^e		X	X	X	X	X	X	X	X	X	X	X
Other lipid parameters ^e			X	X	X	X	X	X	X	X	X	X
Pharmacokinetics												
Plasma sample for total full length ASOs of AZD8233 ^f				X		X	X	X	X	X	X ^f	X
Immunogenicity												
Samples for anti-AZD8233 antibodies ^g			X	X		X		X		X	X ^g	X
Exploratory biomarker analysis												
Biomarker analyses (plasma) ^e	X		X	X	X	X	X	X	X	X	X	X
Biomarker analyses (urine) ^e			X	X	X	X	X	X	X	X	X	X
Genomics Initiative optional, exploratory genetic sample ^h			X									

ADA = antidrug antibody; BMI = body mass index; D = day; ECG = electrocardiogram; EDV = early discontinuation visit; FSH = follicle-stimulating hormone; HbA1c = haemoglobin A1c; hs-CRP = high sensitive C-reactive protein; LDL-C = low-density lipoprotein cholesterol; LH = luteinizing hormone; PCSK9 = proprotein convertase subtilisin/kexin type-9; PK = pharmacokinetic; IMP = Investigational medicinal product

Subjects are required to be fasted for at least 10 hours overnight prior to all study visits except for Visit 1; subjects are permitted to drink water during this period of fasting until 1 hour before blood sampling. On days when subjects attend the clinic in a fasting state, blood and urine samples should be obtained prior to administration of the IMP.

Samples to be obtained from all treatment arms unless specified in the table.

- ^a Weight should be measured in light indoor clothes, without shoes, after using the bathroom. Otherwise, follow the local standard procedure.
- ^b Injection Site Reaction assessments to be collected based on adverse event collection criteria.
- ^c Vital signs and ECG to be measured pre-dose on dosing days.
- ^d Blood samples for complement activation panel will be taken around C_{max} and are to be collected pre-dose and 2 hours (± 5 minutes) post-dose.
- ^e Samples to be obtained pre-dose on dosing days.

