7.2 Clinical Laboratory Assessments

Hematology

WBC count	Neutrophils absolute count
Red blood cell (RBC) count	Lymphocytes absolute count
Hemoglobin (Hb)	Monocytes absolute count
Hematocrit (HCT)	Eosinophils absolute count
Mean corpuscular volume (MCV)	Basophils absolute count
Mean corpuscular haemoglobin concentration (MCHC)	Platelets absolute count
	Reticulocytes absolute count

Clinical Chemistry

Sodium	ALP
Potassium	ALT
Blood urea nitrogen (BUN)	AST
Creatinine	Gamma glutamyl transpeptidase (GGT)
Calcium	Total bilirubin
Phosphate	Direct bilirubin
Creatine kinase (CK)	Glutamate dehydrogenase (GLDH)
Bicarbonate	Lactate dehydrogenase (LDH)
Serum β -human chorionic gonadotropin (β -hCG)(women only)	Uric acid
Luteinizing hormone (LH) (women only)	FSH (women only)
Indirect bilirubin	

Coagulation

aPTT	Prothrombin time
International normalized ratio (INR)	

Urinalysis

Urine human chorionic gonadotropin (hCG) (Women only)

Urinalysis dipstick test

Urinalysis (positive dipstick)

pH	Clarity/Appearance
Specific gravity	Nitrites
Glucose	Ketones
Blood	Leukocytes
Colour	Microscopic analysis (if positive for blood, nitrates or protein)
Protein	Urobilinogen

Urine renal safety biomarkers

Albumin	UPCR
Total protein	UACR
Creatinine	Estimated glomerular filtration rate (eGFR; by the Japanese equation)

Other laboratory assessments

Complement activation panel (Bb, C5a)	High-sensitive C-reactive protein (hs-CRP)
	HbA1c

SIGNATURE PAGE

This is a representation of an electronic record that was signed electronically and this page is the manifestation of the electronic signature

Document Name: d7990c00006-sap-part-b-ed-1		
Document Title:	Statistical Analysis Plan Part B Edition 1	
Document ID:	[REDACTED]	
Version Label:	[REDACTED]	
Server Date (dd-MMM-yyyy HH:mm 'UTC'Z)	Signed by	Meaning of Signature
[REDACTED]	[REDACTED]	Content Approval
[REDACTED]	[REDACTED]	Author Approval
[REDACTED]	[REDACTED]	Content Approval

Notes: (1) Document details as stored in ANGEL, an AstraZeneca document management system.

STATISTICAL ANALYSIS PLAN

Study Code D7990C00006 (Part C)
Edition Number 2.0
Date 3-Nov-2022

**Statistical Analysis Plan for D7990C00006, A Phase 1 and 2
study to evaluate the safety, tolerability, efficacy,
pharmacokinetics and pharmacodynamics of AZD8233
following a multiple subcutaneous dose administration in
Japanese participants with dyslipidemia (HAYATE) – Part C**

TABLE OF CONTENTS

TITLE PAGE.....	1
TABLE OF CONTENTS	2
LIST OF ABBREVIATIONS	5

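### Post-dose complement at later doses is compared only with Day 1, so the acute rise is summed with any chronic drug effect although a same-visit pre-dose sample exists

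*SAP*

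**What the plan says.** **Why complement is measured.** Protocol Section 2.3.1, Table 4, states: "This is a known class effect of oligonucleotides and appears to be directly plasma concentration", with Cmax named as the driver. The mitigation is to assess complement around Cmax. The same entry reports minimal to mild higher Bb at the end of a 9-month monkey study.

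**When it is sampled.** In Part B, "Participants will be dosed subcutaneously on Days 1, 29, and 57". The samples at those visits "are to be collected pre-dose and 2 hours (± 5 minutes) post-dose" (SAP Part B 7.1, footnote d). Parts A and C sample pre-dose and at 1, 2 and 4 h on Days 1 and 57 (Protocol Tables 1 and 3, footnote h).

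**What is derived.** SAP Part B 4.3.5.1 covers complement through the parameter list in Appendix 7.2. It gives one rule: "the change from baseline will be calculated for all post-baseline timepoints as the respective timepoint value minus the baseline value". SAP Parts A and C carry the same rule in 4.2.3.2. Baseline "refers to the last measurement obtained before the first dose of study intervention" (Part B 3.3.1.1; Parts A and C agree), with no exception for complement. The schedules contain no complement sample at screening, and "Pre-dose values on Day 1 qualify as baseline measurements" (Part B 3.3.2), so baseline is the Day 1 pre-dose sample.

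**What is presented.** Values and change from baseline are summarised by treatment group and visit (Part B 4.3.5.2; Parts A and C 4.2.3.4). No SAP defines a difference between a post-dose sample and the pre-dose sample of the same visit.

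**The concern.** The sampling is built to show a rise within hours of a dose. The derived variable does not use that design after Day 1. At later doses it takes the post-dose value and subtracts a value from weeks before.

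Two things could raise that difference: acute activation around Cmax, or a slow shift in the resting level under repeated dosing. Table 4 gives a reason to think about each. If only the resting level moves, the planned post-dose change still shows a rise. If both move, the table does not say how much belongs to each. The participant-level acute rise, with its spread and its outliers, is what a safety reader would want, and it is not tabulated.

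**Working it through.** The plan states no figure for complement (no SD, correlation or expected change), so there is nothing to reproduce.

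**1. Age of the reference used by the SAPs**
- Part B Day 29: 29 − 1 = 28 days = 4.0 weeks. With the ±2-day window, 26 to 30 days (3.7 to 4.3 weeks).
- Part B Day 57: 57 − 1 = 56 days = 8.0 weeks. With ±2 days, 54 to 58 days (7.7 to 8.3 weeks).
- Parts A and C Day 57: 56 days. With ±1 day, 55 to 57 days.

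**2. Age of the same-visit reference**
- Part B: sample at 2 h, pre-dose assessment up to 60 minutes before dosing, so about 2 to 3 h.
- Parts A and C: samples at 1 to 4 h, pre-dose up to 30 minutes before dosing, so about 1 to 4.5 h.

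**3. What each difference estimates**

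Let *a* be the acute rise after a dose, *c* the chronic drug effect on the resting level, and *d* the drift common to both arms. Assume that placebo injection produces no acute rise.

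| Difference at a later dose | Active | Placebo | Active − placebo |
|---|---|---|---|
| Post-dose − Day 1 pre-dose (SAP) | a + d + c | d | a + c |
| Pre-dose − Day 1 pre-dose (SAP) | d + c | d | c |
| Post-dose − same-visit pre-dose (not derived) | a | 0 | a |

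Illustrations in SD units, with assumed values:
- a = 0.5, d = 0.3, c = 0.5: the SAP post-dose change is 0.5 + 0.3 + 0.5 = 1.3 on active and 0.3 on placebo, a difference of 1.0. The same-visit change is 0.5 and 0, a difference of 0.5.
- a = 0, d = 0.3, c = 0.5: the SAP post-dose change is 0.8 on active and 0.3 on placebo, a difference of 0.5, although the true acute rise is 0.
- a = 0.5, d = 0.3, c = 0: 0.8 and 0.3, a difference of 0.5, which is correct. Drift alone does no harm to the comparison with placebo.

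**4. Precision**

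Take a between-day SD equal to *k* times the within-day SD. Then Var(change from Day 1) = 2(between² + within²) and Var(same-visit change) = 2 within², so the SD ratio is √(1 + k²): 1.12 at k = 0.5, 1.41 at k = 1 and 2.24 at k = 2. Equivalently, with correlation r₁ between values weeks apart and r₂ within a visit, the ratio is √((1 − r₁)/(1 − r₂)). For r₁ = r₂ = 0.8 it is 1.0. For r₁ = 0.5 and r₂ = 0.95 it is √(0.5/0.05) = 3.2. Both *k* and the correlations are assumptions, and the range includes no gain.

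**5. Whether both rows reach the tables**

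Section 3.3.2 of each SAP keeps one value per window, the one closest to the scheduled date. All complement samples of a visit share a date, so they tie.
- Part B keeps the later value on a tie and treats the rest as unscheduled. Section 3.3.3 leaves unscheduled values out of by-visit tables. Read literally, the pre-dose rows drop out.
- Parts A and C keep the earlier value on a tie. Read literally, the Day 57 post-dose rows drop out.
- The footnote to Part B Table 1 says that the panel is taken pre-dose only and names Visits 12, 3, 6 and 8. That contradicts the schedule in the same SAP, which has a 2 h post-dose sample and Visits 3, 6 and 8.

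**The case against.** Much can be said for leaving the plan alone.

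- **The baseline follows the protocol.** Section 9.4.1 sets safety baseline as the last value before first dose. The SAPs do not depart from it. This stands: the point asks for an addition.
- **Day 1 is clean.** Its post-dose samples are already compared with a pre-dose sample from the same visit, so a reader who infers that the plan cannot show an acute effect at all goes too far.
- **Placebo is concurrent and on the same schedule.** A reader might infer that drift over 4 to 8 weeks corrupts the comparison. Common drift shows in the placebo column; only the chronic drug effect stays mixed in.
- **The chronic measure exists.** Pre-dose samples at later visits are post-baseline timepoints, so the present rule already gives their change from Day 1.
- **The mean acute rise can be recovered.** If both rows are tabulated, subtracting the two means gives it, exactly so with complete pairs, and individual values are listed. That holds for the mean but not for the SD, the range or the individual rises. It also needs both rows to survive the window rule. SAP Parts A and B (3.3) allow summaries by time point where appropriate, which may rescue them; Part C speaks of study visit.
- **The signal is modest.** Complement is not named in any objective or endpoint, the monkey finding was minimal to mild in a species considered more sensitive, and Protocol Section 2.2 reports no indication of complement activation with more than 120 participants exposed to multiple doses. This limits the weight of the point but does not make the Day 1 reference the better one for an acute effect.

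**Conclusion.** The point holds in a limited form. At Part B Days 29 and 57, and at Day 57 in Parts A and C, the only planned post-dose change estimates a + c against placebo instead of *a*, and no paired within-visit change is defined in any of the three SAPs. The chronic drug effect enters in full, whatever the variances. If it is zero, the comparison with placebo is unbiased for the acute rise.

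A reader might also infer a definite loss of precision. The documents do not support that: they give no complement variance, and under the assumed values above the SD ratio runs from 1.0 to 3.2. Nor is the same-visit sample immediately adjacent to the post-dose draw; it is a few hours older, against 4 or 8 weeks.

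The summaries are descriptive and no test depends on them. The change is still worth making, because the needed samples are already drawn and the one-value-per-window rule, read literally, can remove one side of the comparison from the tables.

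**What to change.** For Bb and C5a, and C3a in Part A:

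1. Add a descriptive by-arm summary of post-dose minus same-visit pre-dose, and of their ratio, at Visits 3, 6 and 8 in Part B and at 1, 2 and 4 h on Days 1 and 57 in Parts A and C.
2. Keep the existing change from Day 1 for the pre-dose samples and label it as the chronic measure.
3. Show pre-dose and each post-dose timepoint as separate rows, exempt from the one-value-per-window rule.
4. Reconcile the Part B Table 1 footnote with the schedule of activities, on both visits and timing.
5. In Part A, whose current SAP edition is already post-database-lock, label the addition as supplementary.

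The cost is one extra derived variable and one table per part. No new samples are needed, and the protocol's safety baseline is untouched.
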